MedDRA	Medical Dictionary for Regulatory Activities
MNTD	maximum number of tolerated doses
MSI	microsatellite instability
MSKCC	Memorial Sloan Kettering Cancer Center
mRECIST	modified Response Evaluation Criteria in Solid Tumors
MTD	maximum tolerated dose
NCI	National Cancer Institute
NE	not evaluable
NSCLC	non-small cell lung cancer
ORR	objective response rate
PAD	pharmacologically active dose

Abbreviation	Term
PD	progressive disease
PD-1	programmed death-1
PD-L1	programmed death ligand-1
PFS	progression-free survival
PK	pharmacokinetic
PP	per protocol
PR	partial response
PT	preferred term
QTcF	QT interval corrected using the Fridericia formula
QRS	QRS is the combination of three of the graphical deflections on an ECG. It is usually the central and most visually obvious part of the tracing. It corresponds to the depolarization of the right and left ventricles of the human heart.
RCC	renal cell carcinoma
RECIST	Response Evaluation Criteria in Solid Tumors
RR	RR is the interval from the beginning of a QRS complex to the beginning of the next QRS complex
SAE	serious adverse event
SAP	Statistical Analysis Plan
SD	stable disease
SI	International System of Units
SOC	system organ class
t	time of last observed quantifiable concentration
TEAE	treatment-emergent adverse event
T _{max}	time of occurrence of C _{max}
WBC	white blood cell
WHO	World Health Organization

1. INTRODUCTION

This is a Phase 1/2, open-label, nonrandomized, multicenter, dose-escalation study. This study will be conducted in 2 parts. Part 1 will utilize a 3 + 3 design to determine the MTD or PAD for INCAGN01949 in subjects with advanced or metastatic solid tumors. Part 2 of the study will further evaluate the safety, tolerability, preliminary efficacy, PK, [REDACTED] of the recommended dose and schedule of INCAGN01949 in subjects with advanced or metastatic adenocarcinoma of the endometrium, ovarian cancer, RCC, melanoma, and NSCLC (squamous and nonsquamous). Section 1 of the Protocol provides a detailed description of the investigational product, target patient population, rationale for doses to be examined, and potential risks and benefits of treatment with INCAGN01949.

The purpose of this SAP is to provide details of the statistical analyses that have been outlined in the Study INCAGN 1949-101 Protocol. The scope of this plan includes the interim and final analyses that are planned and will be executed by the Department of Biostatistics or designee and the analyses of PK. [REDACTED]
[REDACTED].

2. STUDY INFORMATION, OBJECTIVES, AND ENDPOINTS

2.1. Protocol and Case Report Form Version

This SAP is based on INCAGN 1949-101 Protocol dated 07 JUN 2016 and CRFs approved 26 JUL 2016. Unless superseded by an amendment, this SAP will be effective for all subsequent Protocol amendments and CRF versions.

[figure not shown]
2.2. Study Objectives

2.2.1. Primary Objective

- To evaluate the safety, tolerability, and DLTs of INCAGN01949, and to define a MTD or PAD of INCAGN01949 in subjects with metastatic or advanced solid tumors.

2.2.2. Secondary Objectives

- To evaluate the PK of INCAGN01949 in subjects with advanced or metastatic solid tumors.
- To evaluate the preliminary efficacy of INCAGN01949 by assessing the ORR, DOR, PFS, and duration of disease control per RECIST v1.1 and mRECIST v1.1.

[figure not shown]
2.3. Study Endpoints

[figure not shown]
2.3.1. Primary Endpoint

- Safety and tolerability will be assessed by monitoring the frequency, duration, and severity of AEs.

2.3.2. Secondary Endpoints

- The PK of INCAGN01949, including C_{\max} , T_{\max} , C_{\min} , and AUC_{0-t} for subjects in Parts 1 and 2 will be summarized.
- ORR, defined as the percentage of subjects having CR or PR, will be determined by investigator assessment of radiographic disease per RECIST v1.1 and mRECIST v1.1.
- DOR, defined as the time from earliest date of disease response (CR or PR) until earliest date of disease progression, will be determined by investigator assessment of radiographic disease per RECIST v1.1 and mRECIST v1.1, or death from any cause, if occurring sooner than progression.
- PFS, defined as the time from date of first dose of study drug until the earliest date of disease progression, as determined by investigator assessment of objective radiographic disease per RECIST v1.1 and mRECIST v1.1, or death from any cause if occurring sooner than progression.
- Duration of disease control (CR, PR, and SD), as measured from first report of SD or better until disease progression, will be determined by investigator assessment of radiographic disease per RECIST v1.1 and mRECIST v1.1, or death from any cause, if occurring sooner than progression.

3. STUDY DESIGN

[figure not shown]
This is an open-label, nonrandomized, Phase 1/2 study to determine the safety and tolerability, define the MTD or PAD, and assess the preliminary efficacy of INCAGN01949 in subjects with advanced or metastatic solid tumors. Subjects will receive escalating doses of INCAGN01949 on Day 1 of each cycle. Part 1 of the study will begin with 14-day cycles; however, alternate dose administration schedules may also be explored depending on PK, [REDACTED] and safety results. The study will be conducted in 2 parts:

- **Part 1 – Dose Escalation and Safety Expansion** will determine the PAD, defined as a dose that provides a maximal biochemical effect, [REDACTED], and/or the MTD of INCAGN01949, including defining the optimal dose administration schedule and the MNTD.
- **Part 2 – Dose Expansion** will evaluate the recommended dose and administration schedule determined in Part 1 in subjects with select tumor types [REDACTED]

[REDACTED] including adenocarcinoma of endometrium, ovarian cancer, melanoma, NSCLC, and RCC.

See [Figure 1](#) for overall study design.

Figure 1: Study Design

* If Cohort 1 (7 mg) exceeds the MTD, Cohort -1 (2 mg) may be tested and/or Cohort 1 (7 mg) will be tested at alternate dose schedules based on available safety, PK, [REDACTED] data. If an alternate schedule is tested and determined to be safe, re-escalation of INCAGN01949 will proceed as outlined above.

[†] The safety expansion cohorts may evaluate dose(s) and schedule(s) equivalent to or less than the highest dose levels determined to be safe or doses determined to be pharmacologically active. Alternate dose schedules may also be tested depending on PK, [REDACTED] and safety results.

[‡] Subjects in Part 2 will receive the recommended dose determined in Part 1.

3.1. Dose Escalation and Expansion

3.1.1. Part 1 – Dose Escalation

The PAD is defined as a dose that provides a maximal biochemical effect, or an increase in biomarkers of immune activity.

A DLT will be defined as the occurrence of a toxicity, with the exception of events clearly associated with the underlying disease, disease progression, a concomitant medication, or comorbidity; the list of toxicities that will be designated as dose limiting toxicities are provided in Table 3 of the Protocol.

In Part 1 of the study, the MTD will be defined as 1 dose level below that at which \geq one-third of subjects in a particular cohort have DLTs.

In Part 1, subjects with advanced or metastatic solid tumors who progressed after treatment with available therapies that are known to confer clinical benefit, who are intolerant to treatment, or refuse standard treatment will be enrolled.

In the dose-escalation part of the study, a 3 + 3 design will be used to determine the MTD or PAD of INCAGN01949. A minimum of 3 evaluable subjects will be enrolled in each cohort beginning with Cohort 1 (7 mg; starting dose). There will be a waiting period of 48 hours between dose administration of the first subject and second subject of each dose cohort. The first 3 subjects enrolled within a cohort will be observed for a DLT observation period of 28 days

before the next cohort begins enrollment. The dose will be escalated if 0 of the first 3 evaluable subjects enrolled has a DLT. If 1 of the first 3 evaluable subjects enrolled has a DLT, then the cohort will be expanded to include 3 additional evaluable subjects, and if no DLT occurs in the additional 3 subjects, then the dose will be escalated. If a DLT occurs in one-third or more of the expanded cohort, then the MTD will be deemed to be exceeded, and the prior dose level will be considered the MTD. If only 3 subjects were treated at the MTD or PAD, then a minimum of 3 additional subjects will be enrolled before this dose is administered in Part 2 of the study.

If Cohort 1 (7 mg; starting dose) exceeds the MTD, the sponsor and investigators will consider dosing INCAGN01949 at 2 mg (Cohort -1), and/or investigate 7 mg at alternate dose schedules (eg, every 3-week administration), based on available safety, PK, [REDACTED] [REDACTED] data. If an alternate schedule is tested and determined to be safe, re-escalation of INCAGN01949 will proceed according to [Table 1](#).

Throughout the treatment period, if > 33% of subjects (a minimum of 6 subjects) experience a \geq Grade 3 toxicity related to study drug after completing \geq 4 cycles, then dose administration will be stopped, and the MNTD will be determined in conjunction with the investigators and sponsor based on all available safety data.

Additional subjects will be enrolled in a cohort to achieve the minimum of 3 evaluable subjects. Subjects who drop out for reasons other than a DLT (eg, events clearly associated with the underlying disease, disease progression, concomitant medication, or comorbidity) during the 28-day DLT observation period will be considered nonevaluable and will be replaced. Dose modifications should not be made during the DLT observation period without discussion with the medical monitor. Intrasubject dose escalation is not permitted; however, once the recommended dose and schedule have been determined, ongoing subjects in Part 1 may be permitted to escalate the dose to the recommended level with approval of the medical monitor. The cohorts and dose levels are shown in [Table 1](#).

Table 1: INCAGN01949 Dose Levels and Cohort

Cohort	Dose of INCAGN01949 ^a
-1	2 mg ^b
1 (starting dose)	7 mg
2	20 mg
3	70 mg
4	200 mg
5	350 mg
6	700 mg

^a Additional dose schedules may be explored that would depend on PK, [REDACTED], and safety results.

^b Subjects who require a dose reduction below 2 mg should be discontinued from study drug.

3.1.2. Part 1 – Safety Expansion

In order to evaluate additional [REDACTED] activity of INCAGN01949 and confirm the preliminary safety of the dose escalation cohorts, Part 1 of the study may include safety expansion cohorts evaluating doses and schedules equivalent to or lower than the highest dose

levels determined to be safe and/or doses determined to be pharmacologically active. The alternative dose administration schedules and fixed doses (equivalent to or less than the MTD determined during dose escalation) that may be explored during the safety expansion would depend on PK, [REDACTED], and safety results.

A maximum of 36 subjects will be enrolled into the Part 1 safety expansion, and each Part 1 safety expansion cohort will enroll up to 9 evaluable subjects. If < 3 of 9 evaluable subjects have a DLT, then the cohort will be deemed safe. If > 1 safety expansion cohort is deemed safe, then a recommended dose and schedule will be determined in conjunction with the investigators and sponsor based on all available safety, PK, [REDACTED] results. The safety expansion cohorts may be run in parallel to Part 2 and may be limited by the sponsor to subjects with specific tumor types to achieve a balance across cohorts.

3.1.3. Part 2 – Dose Expansion

Part 2 of the study will further evaluate the safety, tolerability, preliminary efficacy, PK, and pharmacologic activity of the recommended dose of INCAGN01949 in subjects with advanced or metastatic adenocarcinoma of the endometrium, melanoma, NSCLC (squamous and nonsquamous), and RCC. Each cohort will comprise an individual tumor type. A Simon 2-stage design (Simon 1989) will be utilized with a stopping rule to allow early termination of a particular cohort at the end of Stage 1 if there are insufficient responses observed. During Stage 1, 9 subjects will be enrolled; if no responses are observed in 16 weeks with 2 scans, then enrollment in the cohort will be terminated. If at least 1 response is observed, then 8 additional subjects will be enrolled into that cohort (Stage 2), for a maximum of 17 subjects per cohort.

Subjects will continue to receive INCAGN01949 until Protocol-defined withdrawal criteria are met. Continuous evaluation of toxicity events will be performed throughout enrollment in Part 2 of the study. If the cumulative incidence of DLTs occurs in $> 33\%$ of subjects after 6 subjects are observed for at least 28 days, further enrollment will be interrupted until the sponsor determines the appropriate course of action. All AEs, regardless of the time of occurrence on study, may be considered in determining the appropriate dose, schedule, and MNTD.

Toxicity will continue to be monitored throughout the treatment period. If $> 33\%$ of subjects (minimum of 6 subjects) experience a Grade ≥ 3 toxicity related to study drug after completing ≥ 4 cycles, then the MNTD will be determined in conjunction with the investigators and sponsor based on all available safety data. All AEs, regardless of the time of occurrence on study, may be considered in DLT determination decisions.

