1.3.3.1.1. Modified RECIST

RECIST v1.1 will be adapted to account for the unique tumor response characteristics seen with immunotherapy ([Chiu and Burotto 2015](#)). Immunotherapeutic agents may produce antitumor effects by potentiating endogenous cancer-specific immune responses. The response patterns seen with such an approach may extend beyond the typical time course of responses seen with cytotoxic agents and can manifest a clinical response after an initial increase in tumor burden or even the appearance of new lesions. Standard RECIST may not provide an accurate response

assessment of immunotherapeutic agents. Therefore, RECIST v1.1 will be used with the following adaptations:

If radiologic imaging shows initial progressive disease, then tumor assessment should be repeated at least 4 weeks but no later than 6 weeks later in order to confirm disease progression with the option of continuing treatment while awaiting radiologic confirmation of progression.

In subjects who have initial evidence of radiological progression but are clinically stable as defined below, it is at the discretion of the treating physician whether to continue a subject on study drug until repeat imaging is obtained. This clinical judgment decision should be based on the subject's overall clinical condition, including performance status, clinical symptoms, and laboratory data. Subjects may receive treatment while waiting for confirmation of disease progression if they are clinically stable as defined by the following criteria:

- Absence of clinically significant signs and symptoms indicating disease progression.
- No decline in ECOG performance status.
- Absence of rapid progression of disease.
- Absence of progressive tumor at critical anatomical sites (eg, cord compression) requiring urgent alternative medical intervention.

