Part 2 of the study will further evaluate the safety, tolerability, preliminary efficacy, PK, and pharmacologic activity of the recommended dose of INCAGN01949. The sample size for each tumor type will be guided by the Simon 2-stage design ([Simon 1989](#)). Let $P_0 = 5\%$ denote a clinically insignificant response rate for all tumor types. In order to determine whether the target response rate (25%) is likely, an initial number of evaluable subjects (9 subjects) treated at the

MTD or PAD and schedule of INCAGN01949 will be enrolled in a cohort (Stage 1). If there is no response for the cohort, it will be concluded that the true response rate is unlikely to be greater than or equal to the target rate, and no more subjects will be enrolled in that tumor type in Stage 2. Due to replacement of subjects for biopsy analysis, additional subjects may be enrolled for the biopsy evaluable population; however, the first 9 evaluable subjects in each cohort will be used for early stopping at Stage 1. In the tumor types in which at least 1 response among the Stage 1 subjects is observed, 8 additional evaluable subjects will be treated in Stage 2 to estimate the response rate. At the end of Stage 2, if ≤ 2 subjects have responded among the evaluable subjects, the drug will be declared nonpromising for that tumor type. In other words, after the study is finished, if there is a sufficient number of responses in the 2 stages combined, the study compound is considered promising; otherwise it is considered nonpromising. The detailed calculation is based on a 1-sided Type I error of 0.05 and power of 80% for each of the tumor types. [Figure 2](#) shows the power to reject the null hypothesis for various response rates.

Figure 2: Power and Type I Error for Simon 2-Stage Design for Various Response Rates

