7.2. Efficacy Hypotheses

Each Simon 2-stage design will test the null hypothesis that the true ORR is less than or equal to the clinically insignificant response rate 5% against the alternative hypothesis that the true ORR is equal to the target ORR of 25%.

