7.4.2. Objective Response Rates and Best Overall Response

A subject is defined as an objective responder if the subject has an overall response of CR or PR at any postbaseline visit before first PD. Objective responders will be assessed based on both RECIST v1.1 and mRECIST v1.1.

Objective response rate is defined as the proportion of subjects with objective responses. Objective response rate will be estimated with 95% CIs overall by cohort-specific tumor type. Confidence intervals will be calculated based on the method for Simon 2-stage CIs of response rates outlined in Koyama and Chen ([Koyama and Chen 2008](#)). Subjects who do not have sufficient baseline or on-study response assessment information to be adequately assessed for response status will be included in the denominators in the calculation of ORR.

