9. INTERIM ANALYSES

There will be no planned, formal interim analyses for the Part 1 dose escalation portion of the study. The review of accrued clinical data will be conducted by Incyte and provided to study investigators via teleconferences at the end of Part 1 of the study. Based on review of the most current safety data, the sponsor (in consultation with the study investigators and using the dose-escalation/de-escalation rules) will determine if and at what dose additional subjects should be treated in the study.

An interim analysis of efficacy will be conducted in Part 2 by applying the Simon 2-stage design. During Stage 1, 9 evaluable subjects treated at the recommended dose and schedule will be enrolled, and if no responses (CR or PR) are observed by the Week 16 assessment (at least 2 scans), then the cohort will be discontinued. The probability of early termination for Stage 1 is summarized in [Table 8](#). If at least 1 response (CR or PR) is observed, then 8 additional subjects will be enrolled for Stage 2. Subject replacement may occur due to the biopsy requirement. In that case, the interim analysis will be conducted with the first 9 evaluable subjects for Stage 1.

[figure not shown]
Per mRECIST v.1.1, the tumor response should be confirmed by a repeat radiographic assessment not less than 4 weeks from the date that the response was first documented. Disease progression will be confirmed by a second tumor assessment in at least 4 weeks and no later than 6 weeks after the first scan indicating PD in clinically stable subjects. The first tumor assessment is conducted at the eighth week. If a CR or PR occurs after an unconfirmed PD in at least 4 weeks but no more than 6 weeks, then the tumor assessment will be counted as a corresponding CR or PR ([Table 4](#)).

Table 8: Probability of Early Termination at Stage 1 for Simon 2-Stage Design

True Response Rate	Probability of Early Termination at Stage 1
15%	23.2%
20%	13.4%
25%	7.5%
30%	4.0%
35%	2.1%

[Figure 3](#) provides the probabilities of early termination with regard to the efficacy analysis of the primary endpoint.

Figure 3: Probabilities of Early Termination for Futility at the End of Simon Stage 1 Based on Various Assumed Rates of Response to a Given Dose Level

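### The SAP's Stage 1 futility rule counts responses only to Week 16 but its final count is untimed, so 7.5% early termination needs essentially all responses by Week 16, and 80% power needs about 93%

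*SAP*

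**What the plan says.** **Stage 1, SAP.** Section 3.1.3 enrolls 9 subjects per tumor type and stops on a timed rule: "if no responses are observed in 16 weeks with 2 scans, then enrollment in the cohort will be terminated". Section 9 repeats it: "if no responses (CR or PR) are observed by the Week 16 assessment (at least 2 scans), then the cohort will be discontinued". With at least one response, "8 additional subjects will be enrolled into that cohort (Stage 2), for a maximum of 17 subjects per cohort".

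**Final count, SAP.** Section 3.4.2 declares the drug nonpromising for a tumor type if 2 or fewer evaluable subjects respond over the two stages, with no time limit. Section 7.4.2 defines a responder as a subject with an "overall response of CR or PR at any postbaseline visit before first PD". Section 7.2 tests an ORR of 5% or less against 25%, again untimed.

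**Operating characteristics.** SAP 3.4.2 says: "The detailed calculation is based on a 1-sided Type I error of 0.05 and power of 80% for each of the tumor types". SAP Table 8 gives 7.5% early termination at a true rate of 25%.

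**Protocol.** The Stage 1 rule in sections 4.1.2, 9.2.2, 9.4.1.1 and 9.6 stops on no responses in 9 subjects and mentions neither Week 16 nor a number of scans. Scans run every 8 weeks for 12 months and then every 12 weeks (7.7.1.1.2). Section 1.3.3.1.1 says that response patterns with immunotherapy "may extend beyond the typical time course of responses seen with cytotoxic agents".

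**The concern.** A Simon design assumes that the response counted at the interim look is the same event as the one counted at the end. Under the SAP it is not. A Stage 1 subject whose first CR or PR comes at the Week 24 scan is a responder for the ORR, but does not count when the cohort's future is decided. If that subject is the only responder among the 9, the cohort has already been closed and nothing in the SAP reopens it.

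The consequence is one-sided. A tumor type with a true ORR of 25% can be closed at Stage 1 more often than SAP Table 8 says, and power is lower than the figure used to justify 9 and 17 subjects. SAP 3.4.2 then concludes from a Stage 1 stop that the true rate is unlikely to reach the target, although the evidence concerns only the rate by Week 16.

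**Working it through.** **Inputs.** Null rate 5%, target 25% (SAP 7.2). n1 = 9, stop at 0 responses; n2 = 8, total 17; 3 or more responses needed (SAP 3.1.3, 3.4.2; Protocol 9.4.1.1). Stage 1 counted to Week 16 (SAP 3.1.3, 9); final count untimed (SAP 7.4.2). The share f of eventual responses first seen by Week 16 is not in the documents, so it is varied.

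**Step 1: reproduce the plan's figures (one rate, f = 1).**

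Early termination = (1 − p)^9. At p = 0.25 this is 0.75^9 = 0.0751, the 7.5% of Table 8. The other rows also reproduce: 23.2%, 13.4%, 4.0% and 2.1% at 15%, 20%, 30% and 35%.

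Probability of declaring the drug promising = Σ over x = 1 to 9 of Bin(x; 9, p) × P(Bin(8, p) ≥ 3 − x).

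- p = 0.25: 0.2253 × 0.6329 (x = 1) + 0.3003 × 0.8999 (x = 2) + 0.3993 (x ≥ 3) = 0.812.
- p = 0.05: 0.2985 × 0.0572 + 0.0629 × 0.3366 + 0.0084 = 0.0466 (from unrounded terms).

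So the design as calculated has 81.2% power and 4.7% type I error, which meets the stated 80% and 0.05.

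**Step 2: apply the Week 16 rule at Stage 1 only.** Suppose each eventual response is seen by Week 16 independently with probability f. Then:

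- Early termination = (1 − p·f)^9.
- Power = Σ over x = 1 to 9 of Bin(x; 9, p) × [1 − (1 − f)^x] × P(Bin(8, p) ≥ 3 − x).

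The bracket is the chance that at least one of the x eventual Stage 1 responders is seen in time. Late Stage 1 responses still count at the end if the cohort went on.

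Example, f = 0.8, p = 0.25: early termination = 0.80^9 = 0.134. Power = 0.2253 × 0.80 × 0.6329 + 0.3003 × 0.96 × 0.8999 + 0.3973 = 0.771.

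| f (assumed) | Early termination at 25% | Power at 25% | Type I error at 5% |
|---|---|---|---|
| 1.00 | 7.5% | 81.2% | 4.7% |
| 0.95 | 8.7% | 80.4% | 4.6% |
| 0.93 | 9.2% | 80.1% | 4.5% |
| 0.90 | 10.1% | 79.5% | 4.5% |
| 0.80 | 13.4% | 77.1% | 4.2% |
| 0.70 | 17.7% | 73.8% | 3.9% |
| 0.60 | 23.2% | 69.4% | 3.6% |

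**Step 3: break-even values.** Setting power to 0.80 gives f = 0.926. Early termination rounds to 7.5% only for f of about 0.998 or more.

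**The case against.** The strongest reply is that the effect may be small. Any futility look needs a cutoff, and naming one is good practice. At f = 0.9 power is 79.5%, only 0.5 points below target, and it stays at or above 78% down to f of about 0.83. The error is also on the conservative side for false positives. SAP 3.3 calls all analyses exploratory and SAP 7.1 makes efficacy secondary. All of this stands and limits the weight of the point. It does not remove it, because the rule still decides which tumor cohorts close.

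The Week 16 wording can also be read more gently. The phrase about at least 2 scans in SAP 9 could mean minimum follow-up, so that subjects enrolled early are observed for longer before the decision and the effective f is higher. The timed wording in both SAP sections reads more naturally as a cutoff, but the text does not settle it. Confirmation works the other way: SAP 9 says an mRECIST response should be confirmed at least 4 weeks later. If Stage 1 counts only confirmed responses, one first seen at Week 16 comes too late and f falls.

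One could also say that 25% was meant as the Week 16 rate. SAP 7.2 and 7.4.2 define the tested ORR without a time limit and do not support that.

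A reader might infer that the Protocol predicts responses after Week 16. It does not. Section 1.3.3.1.1 says that response patterns may extend beyond those seen with cytotoxic agents, and it gives no timing. This makes f < 1 plausible but says nothing about its size.

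**Conclusion.** The point holds for the SAP. If any response first appears after Week 16, its Stage 1 rule does not have the operating characteristics printed beside it. At a true ORR of 25%, power is at least 80% only if about 93% of responses are seen by Week 16. Over f = 0.9 to 0.7, early termination is 10.1% to 17.7% instead of 7.5%, and power is 79.5% to 73.8%. Type I error does not exceed 4.7%.

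Two stronger readings are not supported. First, 93% does not rescue both figures: at f = 0.93 early termination is already 9.2%. Second, Protocol Table 18 is not wrong, because it describes the Protocol's untimed rule correctly. Table 8 in the SAP prints the same numbers beside a different rule. The SAP is dated 05 JAN 2017 and based on the 07 JUN 2016 Protocol (SAP 2.1 and 10), while the Protocol in hand is Amendment 2, so the two Stage 1 rules need reconciling in any case.

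The result rests on 25% being the untimed ORR, on a Week 16 cutoff for every Stage 1 subject, on responses being seen in time independently of each other, and on an assumed f.

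**What to change.** **Preferred.** Reconcile the SAP with the Protocol's untimed rule. State in SAP 3.1.3 and 9 that enrollment pauses at Week 16 if none of the 9 subjects has responded, and that Stage 2 opens if a Stage 1 subject still in follow-up has a CR or PR before a stated cutoff date. The operating characteristics then depend on the share of responses seen by that date, which is at least the Week 16 share. Power moves back toward 81.2%, type I error stays at or below 4.7%, and the maximum remains 17 subjects. No scans beyond the existing schedule are needed. The cost is delay while a cohort is paused, and possibly reopening it. Power returns fully to 81.2% only if no response would come after the cutoff. The same text should say whether a Stage 1 response must be confirmed.

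**If the Week 16 cutoff is kept.** State in SAP 3.4.2 and 9 that 80% and 7.5% assume all responses are seen by Week 16, and add early termination and power for f = 0.7 to 0.9. This costs wording and a less favorable power statement.

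**Not advised.** Do not relabel 5% and 25% as Week 16 rates while the final count stays untimed. The untimed null rate would then be 5%/f. Putting p = 0.05/f into the Step 2 power formula gives a type I error of 5.8% at f = 0.9, 7.3% at f = 0.8 and 9.3% at f = 0.7, above the stated 0.05.
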